### **Specifications by methods of measurements**

#### **Measurement of lesions**

All measurements should be recorded in metric notation, using calipers if clinically assessed. All baseline evaluations should be performed as close as possible to the treatment start and never more than 4 weeks before the beginning of the treatment.

#### **Method of assessment**

The same method of assessment and the same technique should be used to characterize each identified and reported lesion at baseline and during follow-up. Imaging based evaluation should always be done rather than clinical examination unless the lesion(s) being followed cannot be imaged but are assessable by clinical exam.

Clinical lesions: Clinical lesions will only be considered measurable when they are superficial and  $\geq 10$  mm diameter as assessed using calipers (e.g., skin nodules). For the case of skin lesions, documentation by color photography including a ruler to estimate the size of the lesion is suggested. As noted above, when lesions can be evaluated by both clinical exam and imaging, imaging evaluation should be undertaken since it is more objective and may also be reviewed at the end of the study.

Chest X-ray: Chest CT is preferred over chest X-ray, particularly when progression is an important endpoint, since CT is more sensitive than X-ray, particularly in identifying new lesions. However, lesions on chest X-ray may be considered measurable if they are clearly defined and surrounded by aerated lung. Still, non-contrast CT is preferred over chest X-ray.

CT, MRI: CT is the best currently available and reproducible method to measure lesions selected for response assessment. This guideline has defined measurability of lesions on CT scan based on the assumption that CT slice thickness is 5 mm or less. When CT scans have slice thickness greater than 5 mm, the minimum size for a measurable lesion should be twice the slice thickness. MRI is also acceptable in certain situations (e.g., for body scans).

If prior to enrolment it is known that a patient is not able to undergo CT scans with IV contrast due to allergy or renal insufficiency, the decision as to whether a non-contrast CT or MRI (with or without IV contrast) will be used to evaluate the patient at baseline and follow-up, should be guided by the tumor type under investigation and the anatomic location of the disease. For patients who develop contraindications to contrast after baseline contrast CT is done, the decision as to whether non-contrast CT or MRI (enhanced or non-enhanced) will be performed, should also be based on the tumor type, anatomic location of the disease and should be optimized to allow for comparison to the prior studies if possible. Each case should be discussed with the radiologist to determine if substitution of these other approaches is possible and, **if not, the patient should be considered not evaluable from that point forward.**

Ultrasound: Ultrasound is not useful in assessment of lesion size and should not be used as a method of measurement. Ultrasound examinations cannot be reproduced in their entirety for independent review at a later date and, because they are operator dependent, it cannot be guaranteed that the same technique and measurements will be taken from one assessment to the next. If new lesions are identified by ultrasound in the course of the study, confirmation by CT or MRI is advised. If there is concern about radiation exposure at CT, MRI may be used instead of CT in selected instances.

Endoscopy, laparoscopy: The utilization of these techniques for objective tumor evaluation is not advised. However, they can be useful to confirm complete pathological response when biopsies are obtained or to determine relapse in trials where recurrence following complete response or surgical resection is an endpoint.

Tumor markers: Tumor markers alone cannot be used to assess objective tumor response. If markers are initially above the upper normal limit, however, they must normalize for a patient to be considered in complete response. Because tumor markers are disease specific, instructions for their measurement should be incorporated into protocols on a disease specific basis. Specific guidelines for both CA-125 response (in recurrent ovarian cancer) and PSA response (in recurrent prostate cancer), have been published. In addition, the Gynecologic Cancer Intergroup has developed CA-125 progression criteria which are to be integrated with objective tumor assessment for use in first-line trials in ovarian cancer.

Cytology, histology: These techniques can be used to differentiate between PR and CR in rare cases if required by protocol (for example, residual lesions in tumor types such as germ cell tumors, where known residual benign tumors can remain). When effusions are known to be a potential adverse effect of treatment (e.g., with certain taxane compounds or angiogenesis inhibitors), the cytological confirmation of the neoplastic origin of any effusion that appears or worsens during treatment can be considered if the measurable tumor has met criteria for response or stable disease in order to differentiate between response (or stable disease) and progressive disease.

## **Tumor response evaluation**

### **Assessment of overall tumor burden and measurable disease**

To assess objective response or future progression, it is necessary to estimate the overall tumor burden at baseline and use this as a comparator for subsequent measurements. Only patients with measurable disease at baseline should be included in protocols where objective tumor response is the primary endpoint. Measurable disease is defined by the presence of at least one measurable lesion. In studies where the primary endpoint is tumor progression (either time to progression or proportion with progression at a fixed date), the protocol must specify if entry is restricted to those with measurable disease or whether patients having non-measurable disease only are also eligible.

### **Baseline documentation of ‘target’ and ‘non-target’ lesions**

When more than one measurable lesion is present at baseline all lesions up to a maximum of five lesions total (and a maximum of two lesions per organ) representative of all involved organs should be identified as target lesions and will be recorded and measured at baseline.

This means in instances where patients have only one or two organ sites involved a maximum of two (one site) and four lesions (two sites), respectively, will be recorded. Other lesions in that

organ will be recorded as non-measurable lesions (even if size is greater than 10 mm by CT scan).

Target lesions should be selected on the basis of their size (lesions with the longest diameter), be representative of all involved organs, but in addition should be those that lend themselves to reproducible repeated measurements. It may be the case that, on occasion, the largest lesion does not lend itself to reproducible measurement in which circumstance the next largest lesion which can be measured reproducibly should be selected.

Lymph nodes merit special mention since they are normal anatomical structures which may be visible by imaging even if not involved by tumor. Pathological nodes which are defined as measurable and may be identified as target lesions must meet the criterion of a short axis of  $\geq 15$  mm by CT scan. Only the short axis of these nodes will contribute to the baseline sum. The short axis of the node is the diameter normally used by radiologists to judge if a node is involved by solid tumor. Nodal size is normally reported as two dimensions in the plane in which the image is obtained (for CT scan this is almost always the axial plane; for MRI the plane of acquisition may be axial, sagittal or coronal). The smaller of these measures is the short axis. For example, an abdominal node which is reported as being 20 mm x 30 mm has a short axis of 20 mm and qualifies as a malignant, measurable node. In this example, 20 mm should be recorded as the node measurement. All other pathological nodes (those with short axis  $\geq 10$  mm but  $< 15$  mm) should be considered non-target lesions. Nodes that have a short axis  $< 10$  mm are considered non-pathological and should not be recorded or followed.

A sum of the diameters (longest for non-nodal lesions, short axis for nodal lesions) for all target lesions will be calculated and reported as the baseline sum diameters. If lymph nodes are to be included in the sum, then as noted above, only the short axis is added into the sum. The baseline sum diameters will be used as reference to further characterize any objective tumor regression in the measurable dimension of the disease.

All other lesions (or sites of disease) including pathological lymph nodes should be identified as non-target lesions and should also be recorded at baseline. Measurements are not required and these lesions should be followed as 'present', 'absent', or in rare cases 'unequivocal progression.' In addition, it is possible to record multiple non-target lesions involving the same organ as a single item on the case report form (e.g., 'multiple enlarged pelvic lymph nodes' or 'multiple liver metastases').

### **Response criteria**

This section provides the definitions of the criteria used to determine objective tumor response for target lesions.

### **Evaluation of target lesions**

- **Complete Response (CR):** Disappearance of all target lesions. Any pathological lymph nodes (whether target or non-target) must have reduction in short axis to < 10 mm.
- **Partial Response (PR):** At least a 30% decrease in the sum of diameters of target lesions, taking as reference the baseline sum diameters.
- **Progressive Disease (PD):** At least a 20% increase in the sum of diameters of target lesions, taking as reference the smallest sum on study (this includes the baseline sum if that is the smallest on study). In addition to the relative increase of 20%, the sum must also demonstrate an absolute increase of at least 5 mm. (Note: the appearance of one or more new lesions is also considered progression).
- **Stable Disease (SD):** Neither sufficient shrinkage to qualify for PR nor sufficient increase to qualify for PD, taking as reference the smallest sum diameters while on study.

### Special notes on the assessment of target lesions

**Lymph nodes:** Lymph nodes identified as target lesions should always have the actual short axis measurement recorded (measured in the same anatomical plane as the baseline examination), even if the nodes regress to below 10 mm on study. This means that when lymph nodes are included as target lesions, the ‘sum’ of lesions may not be zero even if complete response criteria are met, since a normal lymph node is defined as having a short axis of < 10 mm. Case report forms or other data collection methods may therefore be designed to have target nodal lesions recorded in a separate section where, in order to qualify for CR, each node must achieve a short axis < 10 mm. For PR, SD, and PD, the actual short axis measurement of the nodes is to be included in the sum of target lesions.

**Target lesions that become ‘too small to measure’:** While on study, all lesions (nodal and non-nodal) recorded at baseline should have their actual measurements recorded at each subsequent evaluation, even when very small (e.g., 2 mm). However, sometimes lesions or lymph nodes which are recorded as target lesions at baseline become so faint on CT scan that the radiologist may not feel comfortable assigning an exact measure and may report them as being ‘too small to measure’. When this occurs it is important that a value be recorded on the case report form:

- If it is the opinion of the radiologist that the lesion has likely disappeared, the measurement should be recorded as 0 mm. If the lesion is believed to be present and is faintly seen but too small to measure, a default value of 5 mm should be assigned and BML (below measurable limit) should be ticked (Note: It is less likely that this rule will be used for lymph nodes since they usually have a definable size when normal and are frequently surrounded by fat such as in the retroperitoneum; however, if a lymph node is believed to be present and is faintly seen but too small to measure, a default value of 5 mm should be assigned in this circumstance as well and BML should also be ticked).

This default value is derived from the 5 mm CT slice thickness (but should not be changed with varying CT slice thickness). The measurement of these lesions is potentially non-reproducible, therefore providing this default value will prevent false responses or progressions based upon measurement error.

**To reiterate, however, if the radiologist is able to provide an actual measure, that should be recorded, even if it is below 5 mm and in that case BML should not be ticked. (BML is equivalent to a less than sign <)**

Lesions that split or coalesce on treatment: When non-nodal lesions ‘fragment’, the longest diameters of the fragmented portions should be added together to calculate the target lesion sum. Similarly, as lesions coalesce, a plane between them may be maintained that would aid in obtaining maximal diameter measurements of each individual lesion. If the lesions have truly coalesced such that they are no longer separable, the vector of the longest diameter in this instance should be the maximal longest diameter for the ‘coalesced lesion’.

### **Evaluation of non-target lesions**

This section provides the definitions of the criteria used to determine the tumor response for the group of non-target lesions. While some non-target lesions may actually be measurable, they need not be measured and instead should be assessed only qualitatively at the time points specified in the protocol.

Complete Response (CR): Disappearance of all non-target lesions and normalization of tumor marker level. All lymph nodes must be non-pathological in size (< 10 mm short axis).

Non-CR/Non-PD: Persistence of one or more non-target lesion(s) and/or maintenance of tumor marker level above the normal limits.

Progressive Disease (PD): Unequivocal progression of existing non-target lesions. (Note: the appearance of one or more new lesions is also considered progression).

### **Special notes on assessment of progression of non-target disease**

The concept of progression of non-target disease requires additional explanation as follows:

When the patient also has measurable disease: **In this setting, to achieve ‘unequivocal progression’ on the basis of the non-target disease, there must be an overall level of substantial worsening in non-target disease in a magnitude that, even in presence of SD or PR in target disease, the overall tumor burden has increased sufficiently to merit discontinuation of therapy.** A modest ‘increase’ in the size of one or more non-target lesions is usually not sufficient to qualify for **unequivocal progression** status. The designation of overall progression solely on the basis of change in non-target disease in the face of SD or PR of target disease will therefore be extremely rare.

When the patient has only non-measurable disease: This circumstance arises in some phase III trials when it is not a criterion of study entry to have measurable disease. The same general concepts apply here as noted above; however, in this instance there is no measurable disease assessment to factor into the interpretation of an increase in non-measurable disease burden. Because worsening in non-target disease cannot be easily quantified (by definition: if all lesions are truly non-measurable) a useful test that can be applied when assessing patients for unequivocal progression is to consider if the increase in overall disease burden based on the change in non-measurable disease is comparable in magnitude to the increase that would be required to declare PD for measurable disease: i.e., an increase in tumor burden representing an additional 73% increase in ‘volume’ (which is equivalent to a 20% increase diameter in a measurable lesion). Examples include an increase in a pleural effusion from ‘trace’ to ‘large’, an increase in lymphangitic disease from localized to widespread, or may be described in protocols as ‘**sufficient to require a change in therapy**’. If ‘unequivocal progression’ is seen, the patient should be considered to have had overall PD at that point. While it would be ideal to have objective criteria to apply to non-measurable disease, the very nature of that disease makes it impossible to do so; therefore the increase must be **substantial**.

### **New lesions**

The appearance of new malignant lesions denotes disease progression; therefore, some comments on detection of new lesions are important. There are no specific criteria for the identification of new radiographic lesions; however, the finding of a new lesion should be unequivocal: i.e., not attributable to differences in scanning technique, change in imaging modality or findings thought to represent something other than tumor (for example, some ‘new’ bone lesions may be simply healing or flare of pre-existing lesions). This is particularly important when the patient’s baseline lesions show partial or complete response. For example, necrosis of a liver lesion may be reported on a CT scan report as a ‘new’ cystic lesion, which it is not.

A lesion identified on a follow-up study in an anatomical location that was not scanned at baseline is considered a new lesion and will indicate disease progression. An example of this is the patient who has visceral disease at baseline and while on study has a brain CT or MRI ordered which reveals metastases. The patient’s brain metastases are considered to be evidence of PD even if he/she did not have brain imaging at baseline.

If a new lesion is equivocal, for example because of its small size, continued therapy and follow-up evaluation will clarify if it represents truly new disease. If repeat scans confirm there is definitely a new lesion, then progression should be declared using the date of the initial scan.

**(18)F-Fluorodeoxyglucose Positron Emission Tomography (FDG-PET)** For the purposes of this study, progressive disease *should not* be made solely on FDG-PET findings because the mechanism of the study drug, CB-839, may affect glucose metabolism in both normal and tumor tissues. All FDG-PET findings suggestive of progressive disease should be confirmed by

dedicated anatomic imaging (CT or MRI). The following modifications to RECIST v1.1. will be applied to this study:

- Negative FDG-PET at baseline, with a positive FDG-PET at follow-up is a sign of PD based on a new lesion. \*Confirmation of the new lesion by CT or MRI scan is required per protocol.
- No FDG-PET at baseline and a positive FDG-PET at follow-up:
  - If the positive FDG-PET at follow-up corresponds to a new sign of disease confirmed by CT, this is PD
  - If the positive FDG-PET at follow-up is not confirmed as a new site of disease on CT, additional follow-up CT scans are needed to determine if there is truly progression occurring at that site (if so, the date of PD will be the date of the initial abnormal \*CT scan).
  - If the positive FDG-PET at follow-up corresponds to a pre-existing site of disease on CT that is not progressing on the basis of the anatomic images, this is not PD.

\*reflects study-specific modification to RECIST v.1.1

### **Evaluation of best overall response**

The best overall response is the best response recorded from the start of the study treatment until the end of treatment taking into account any requirement for confirmation. On occasion a response may not be documented until after the end of therapy so protocols should be clear if post-treatment assessments are to be considered in determination of best overall response. Protocols must specify how any new therapy introduced before progression will affect best response designation. The patient's best overall response assignment will depend on the findings of both target and non-target disease and will also take into consideration the appearance of new lesions. Furthermore, depending on the nature of the study and the protocol requirements, it may also require confirmatory measurement. Specifically, in nonrandomized trials where response is the primary endpoint, confirmation of PR or CR is needed to deem either one the 'best overall response'. This is described further below.

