**6.6 Radiological Tumor Assessments**

All patients will be evaluated for tumor response assessed by Investigator according to both RECIST version 1.1 and modified RECIST for immune-based therapeutics (termed iRECIST) (Seymour 2017). The primary study endpoints of response rate and duration of response will be determined according to RECIST v1.1 by Investigator assessment except for Cohort 4 which will employ IRC adjudication for the primary endpoints. *In contrast to the formal study endpoints, patient management and clinical decision making during treatment should follow the principles and guidelines for iRECIST (Attachment 5).* These criteria take into account the observation that some patients with solid tumors can have an apparent radiographic flare of disease on immunotherapy that is transient and followed by radiographic disease response. If imaging shows progressive disease per RECIST v1.1 (unconfirmed PD per iRECIST), it is recommended to keep the patient on study treatment until imaging is repeated  $\geq 4$  weeks later in order to confirm PD, as described in the iRECIST recommendations (see Attachment 5). Patients who are deemed clinically unstable or are experiencing rapid progression of disease are not required to have repeat imaging for confirmation of PD. At a minimum, patients must meet the following criteria for continued treatment on study after disease progression is identified at a tumor assessment:

- Absence of symptoms and signs (including worsening of laboratory values) indicating disease progression
- No decline in ECOG performance status
- Absence of rapid progression of disease or of tumor progression at critical anatomical sites (e.g., cord compression) requiring urgent alternative medical intervention.

If repeat imaging confirms PD as described in [Attachment 5](#), patients will be discontinued from study therapy. If repeat imaging does not confirm PD, treatment with study drugs will continue and the next imaging studies will be conducted every 8 weeks as previously scheduled. In patients who discontinue study therapy early without documented disease progression, every effort should be made to continue monitoring disease status by radiologic imaging until progressive disease, death, withdrawal of consent, or initiation of new anticancer therapy.

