#### **Best overall response: All time points**

The best overall response (Table C) will be determined by statistical programming once all the data for the patient are known.

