For equivocal findings of progression (e.g., very small and uncertain new lesions; cystic changes or necrosis in existing lesions), treatment may continue until the next scheduled assessment. If at the next scheduled assessment, progression is confirmed, the date of progression should be the earlier date when progression was suspected

**ATTACHMENT 5: iRECIST: MODIFIED RECIST 1.1 FOR IMMUNE-BASED THERAPEUTICS***(Source: Seymour 2017)*

A consensus guideline—iRECIST—was developed by the RECIST working group for the use of modified Response Evaluation Criteria in Solid Tumors (RECIST version 1.1) in cancer immunotherapy trials, to ensure consistent design and data collection, facilitate the ongoing collection of trial data, and ultimate validation of the guideline. This guideline describes a standard approach to solid tumor measurements and definitions for objective change in tumor size for use in trials in which an immunotherapy is used. A comparison of RECIST and iRECIST is shown in Table S1 below,

	RECIST 1.1	iRECIST
Definitions of measurable and non-measurable disease; numbers and site of target disease	Measurable lesions are $\geq 10$ mm in diameter ( $\geq 15$ mm for nodal lesions); maximum of five lesions (two per organ); all other disease is considered non-target (must be $\geq 10$ mm in short axis for nodal disease)	No change from RECIST 1.1; however, new lesions are assessed as per RECIST 1.1 but are recorded separately on the case report form (but not included in the sum of lesions for target lesions identified at baseline)
Complete response, partial response, or stable disease	Cannot have met criteria for progression before complete response, partial response, or stable disease	Can have had iUPD (one or more instances), but not iCPD, before iCR, iPR, or iSD
Confirmation of complete response or partial response	Only required for non-randomised trials	As per RECIST 1.1
Confirmation of stable disease	Not required	As per RECIST 1.1
New lesions	Result in progression; recorded but not measured	Results in iUPD but iCPD is only assigned on the basis of this category if at next assessment additional new lesions appear or an increase in size of new lesions is seen ( $\geq 5$ mm for sum of new lesion target or any increase in new lesion non-target); the appearance of new lesions when none have previously been recorded, can also confirm iCPD

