- 2.3 *Target Lesions.* When more than one measurable tumor lesion is present at baseline all lesions up to a maximum of 5 lesions total (and a maximum of 2 lesions per organ) representative of all involved organs should be identified as target lesions and will be recorded and measured at baseline. Target lesions should be selected on the basis of their size (lesions with the longest diameter), be representative of all involved organs, but in addition should be those that lend themselves to reproducible repeated measurements. Note that pathological nodes must meet the criterion of a short axis of  $\geq 15$  mm by CT scan and only the short axis of these nodes will contribute to the baseline sum. All other pathological nodes (those with short axis  $\geq 10$  mm but  $< 15$  mm) should be considered non-target lesions. Nodes that have a short axis  $< 10$  mm are considered non-pathological and should not be recorded or followed. At baseline, the sum of the target lesions (longest diameter of tumor lesions plus short axis of lymph nodes: overall maximum of 5) is to be recorded.

After baseline, a value should be provided on the CRF for all identified target lesions for each assessment, even if very small. If extremely small and faint lesions cannot be accurately measured but are deemed to be present, a default value of 5 mm may be used. If lesions are too small to measure and indeed are believed to be absent, a default value of 0 mm may be used.

- 2.4 Non-target Lesions. All non-measurable lesions (or sites of disease) plus any measurable lesions over and above those listed as target lesions are considered *non-target lesions*. Measurements are not required but these lesions should be noted at baseline and should be followed as “present” or “absent”.
- 2.5 Response. All patients will have their BEST RESPONSE from the start of study treatment until the end of treatment classified as outlined below and shown in Table S2:

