- 6.4 Ultrasound. Ultrasound is not useful in assessment of lesion size and should not be used as a method of measurement. If new lesions are identified by ultrasound in the course of the study, confirmation by CT is advised.
- 6.5 Endoscopy, Laparoscopy. The utilization of these techniques for objective tumor evaluation is not advised. However, they can be useful to confirm complete pathological response when biopsies are obtained or to determine relapse in trials where recurrence following complete response or surgical resection is an endpoint.
- 6.6 Tumor Markers. Tumor markers alone cannot be used to assess objective tumor response. If markers are initially above the upper normal limit, however, they must normalize for a patient to be considered in complete response.
- 6.7 Cytology, Histology. These techniques can be used to differentiate between PR and CR in rare cases if required by protocol (for example, residual lesions in tumor types such as germ cell tumors, where known residual benign tumors can remain). When effusions are known to be a potential adverse effect of treatment (e.g., with certain taxane compounds or angiogenesis inhibitors), the cytological confirmation of the neoplastic origin of any effusion that appears or worsens during treatment when the measurable tumor has met criteria for response or stable disease is advised to differentiate between response or stable disease and progressive disease.
8. Examples of scenarios  
The tables below exhibit various response scenarios using iRECIST.

Scenario A						
	Baseline	TP1	TP2	TP3	TP4	TP5
T lesions (sum)	100	125	125	125	-	-
NT lesions	PRES	UC	UC	UNE	-	-
New lesions	-	ABS	ABS	ABS	-	-
TP response (R)	-	PD	PD	PD	-	-
TP response (iR)	-	iUPD	iUPD	iCPD	-	-
RECIST 1.1 has PD at TP1. iRECIST has iUPD at TP1, iCPD at TP3 and iBOR of iCPD. iPD date=TP1. iCPD is based on NEW RECIST 1.1 PD in NT disease. Follow up past iCPD is recommended at TP4 and TP5 unless other systemic or local treatment started.						

Scenario B						
	Baseline	TP1	TP2	TP3	TP4	TP5
T lesions (sum)	100	125	50	50	50	120
NT lesions	PRES	UC	UC	UC	UC	UC
New lesions		+	UC	UC	++	+*
TP response (R)		PD	PD	PD	PD	PD
TP response (iR)		iUPD	iPR**	iPR**	iUPD	iCPD
* some NLs resolve. ** iPR despite non-resolution of new lesions detected at TP2. RECIST 1.1 has PD at TP1. iRECIST has iUPD at TP1 and TP4, iCPD at TP5 and iBOR of iPR. iCPD is based on RECIST 1.1 defined PD in T disease. iPD date = TP4						

Scenario C						

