## **7.7 Changes in the Conduct of the Study or Planned Analyses**

The SAP version 2.0 is amended from version 1.0 to remove restriction on the primary end point for Cohort 4 so that Cohort 4 is investigator assessed, rather than IRC assessed. That is, the primary end point for Cohort 4 is the same as the other cohorts. This decision was made by the sponsor Calithera.

SAP version 2.0 also removes references to Cohort 6 because this cohort was never enrolled.

SAP version 2.0 does not require the summarization of protocol deviations because protocol deviations may not be sufficiently standardized to allow for summarization. Though referenced in the study protocol, no iRECIST analyses are to be conducted per the SAP.

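### Attachment 4 and SAP 7.4.1 do not stop best overall response at the first RECIST 1.1 progression, while Attachment 5 Table S1 bars any later response, so the documents conflict on the primary ORR

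*Protocol*

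**What the plan says.** Protocol 6.6 separates patient management, which follows iRECIST, from the formal endpoints, which follow RECIST 1.1. When imaging shows RECIST 1.1 progression, "it is recommended to keep the patient on study treatment until imaging is repeated" at least 4 weeks later. If the repeat scan does not confirm progression, treatment and 8-weekly imaging go on. Scans after a RECIST 1.1 PD are therefore expected.

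These places define RECIST 1.1 response without a stop at first PD:

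- Attachment 4, in its text on the response window: "The best overall response is the best response recorded from the start of the study treatment until the end of treatment", subject to confirmation.
- Attachment 4, target lesions: PR is "At least a 30% decrease in the sum of diameters of target lesions, taking as reference the baseline sum diameters", so it is measured from baseline whatever happened in between.
- Attachment 4, all time points: best overall response "will be determined by statistical programming once all the data for the patient are known". Table C, which governs this, has no row in which PD comes first.
- Attachment 5 section 2.5, for RECIST 1.1: "All patients will have their BEST RESPONSE from the start of study treatment until the end of treatment classified as outlined below".
- Protocol 16.5 and SAP 7.4.1: CR or PR by RECIST 1.1, confirmed at 4 weeks or later. Neither requires the response to come before PD.

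These places say the opposite for RECIST 1.1:

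- Attachment 5 Table S1, RECIST 1.1 column, row for CR, PR or SD: "Cannot have met criteria for progression before complete response, partial response, or stable disease".
- Attachment 5, Scenario D: after PD at the third time point, the RECIST 1.1 rating stays PD at the fourth and fifth, although the target sum is back to 50 from a baseline of 100 and the new lesion is gone.

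SAP 7.7 adds that "no iRECIST analyses are to be conducted per the SAP".

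**The concern.** The protocol anticipates flare followed by shrinkage and keeps such patients on treatment and under imaging. For those patients the documents give two answers to the question that decides the primary endpoint: is a confirmed PR that follows a RECIST 1.1 PD a response? A programmer working from Attachment 4 and SAP 7.4.1 would count it; one who gives effect to Table S1 would not.

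The other endpoints would then disagree within one patient. SAP 7.4.2 dates the PFS event at the earliest progression. For DOR, SAP 7.4.1 applies the Table 2 rules only to assessments after first response, so it would not see the earlier PD. The patient would have a PFS event and, at a later date, the start of a response.

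At stake are single-arm decisions on small counts against background rates of 5% to 25%, with the primary endpoint investigator-assessed in every cohort under SAP 5.2.1.1.

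**Working it through.** **1. One patient under each rule.** Take target sums of 100 (baseline), 125, 65 and 60, non-target disease not progressing, no new lesions, and the last two scans at least 4 weeks apart.

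| Scan | Check (Attachment 4) | Table A rating |
|---|---|---|
| 125 | (125 − 100)/100 = +25% from the smallest sum, and +25 mm | PD |
| 65 | (100 − 65)/100 = 35% below baseline; no rise from the smallest sum | PR |
| 60 | (100 − 60)/100 = 40% below baseline | PR |

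Under Attachment 4 and SAP 7.4.1 this is a confirmed PR. Under Table S1 it is not a response, because PD was met first.

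**2. The scenarios as a cross-check.** Scenario D at the fourth time point has a sum of 50 against a baseline of 100, non-target disease unchanged and no new lesion. Table A gives PR; the scenario records PD. The two scoring rules therefore differ on identical data. Scenario B ("RECIST 1.1 has PD at TP1. iRECIST has iUPD at TP1 and TP4, iCPD at TP5 and iBOR of iPR") separates them less well: its new lesion is still present when the sum falls to 50, so Table A also gives PD there.

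**3. The plan's own figure for Cohort 4.** SAP 5.3 says the 95% CI for 14/75 excludes 10%. SAP 7.4.1 specifies Clopper-Pearson: lower limit = 2.5% quantile of Beta(x, n − x + 1), upper limit = 97.5% quantile of Beta(x + 1, n − x).

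- x = 14: 14/75 = 18.7%, CI 10.6% to 29.3%. This excludes 10%, as stated.
- x = 13: 13/75 = 17.3%, CI 9.6% to 27.8%. This does not exclude 10%.

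If one of 14 responders first responded after PD, the two readings give opposite conclusions. The same holds at the rejection boundaries of 3/24 (Cohort 3), 5/56 (Cohorts 2 and 5) and 17/52 (Cohort 1).

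**4. Illustration only.** For the two-stage designs, P(reject | p) = Σ over x from r1 + 1 to n1 of b(x; n1, p) × P[Bin(n − n1, p) ≥ r2 + 1 − x]. At the background rates this reproduces the planned error rates: 0.099 (Cohort 1), 0.097 (Cohorts 2 and 5) and 0.093 (Cohort 3), with power 0.800, 0.801 and 0.805. For Cohort 4, P(X ≥ 14 of 75) at 10% is 0.016. If post-PD responses added 1, 2 or 5 percentage points to an ORR that truly equals background (an assumption; the documents give no such rate):

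| Cohort | Planned | +1 point | +2 points | +5 points |
|---|---|---|---|---|
| 1 | 0.10 | 0.13 | 0.17 | 0.31 |
| 2 and 5 | 0.10 | 0.16 | 0.24 | 0.50 |
| 3 | 0.09 | 0.14 | 0.19 | 0.36 |
| 4 (14/75 against 10%) | 0.02 | 0.03 | 0.06 | 0.23 |

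**The case against.** The strongest reply is that the rule already exists. The Table S1 entry is written for RECIST 1.1, the endpoints are defined by RECIST 1.1, and Protocol 6.6 expressly separates continued treatment from endpoint scoring. Attachment 4 never says that a response after PD counts. Since Attachment 5 contains both the start-to-end window and the bar, the window can be read as an outer frame inside which the bar operates. That reading is reasonable, and a programmer used to RECIST would probably adopt it. It does not remove the conflict: Table A and Scenario D still rate the same data differently, and the SAP section that governs the analysis is silent.

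The objection to size also stands. A persisting new lesion keeps the rating at PD under Table A, so the gap mainly concerns target-lesion growth that later shrinks, or new lesions that resolve. Protocol 6.6 requires no signs or symptoms of progression, no ECOG decline and no rapid progression for treatment to continue, and stops treatment once PD is confirmed. The later response must itself be confirmed. An added 5 points would double the 5% background in Cohorts 2, 3 and 5, which is hard to credit. And one patient can flip a boundary result under any kind of misclassification.

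A reader might also infer that dropping iRECIST in SAP 7.7 is what lets post-PD responses into the ORR. It does not: cancelling an exploratory analysis leaves the RECIST 1.1 bar in Table S1 in force. Its effect is that such responses have no separate table of their own. Nor does Scenario D show a patient being denied a response: that patient had PR at two time points before PD. It shows only that PD is carried forward.

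**Conclusion.** The conflict is real and bears on the primary ORR and DOR. Attachment 4, Attachment 5 section 2.5 and SAP 7.4.1, applied literally, allow a confirmed PR after RECIST 1.1 PD to count; Attachment 5 Table S1 and Scenario D do not. It is a contradiction to be settled, not a missing rule, and it affects few patients.

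The result that needs no assumption about frequency is the boundary case: one reclassified patient moves Cohort 4 from excluding 10% (14/75) to not excluding it (13/75). A reader might infer from the illustrative table that false-positive rates will rise as high as 0.50. The documents do not support that, because they give no rate of response after progression; the table shows sensitivity only. The point should be corrected, but it does not undermine the design.

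**What to change.** Add to SAP 7.4.1: for RECIST 1.1 best overall response, ORR and DOR, only assessments up to and including the first RECIST 1.1 PD are used, and a CR or PR first met after that PD is not a response. Amend the best-response window in Attachment 4 and in Attachment 5 section 2.5 to match Table S1.

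Responses seen after PD can be given in a separate listing. Restoring the full iRECIST analysis is optional; SAP 7.7 discloses its removal, and that removal is not part of this error.

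The cost is one SAP sentence and two wording alignments, using data already collected. The downside is that the ORR may be slightly lower.
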